In Part A, the study population will be comprised of male and female patients with partial thickness cartilage lesions of one knee. A total of approximately 60 patients will be enrolled in the study and randomized. Randomization will be stratified by type of lesion (femoral condyle or patella). At least 48 patients are expected to complete the study (20% drop out rate). Additional patients may be enrolled if the dropout rate will exceed 20%.

The investigator must ensure that all patients included in the study meet the eligibility criteria. No additional criteria should be applied by the investigator, in order that the study population will be representative of all eligible patients. Patient selection is to be established by checking through all eligibility criteria at screening and before dosing. A relevant record (e.g. checklist) of the eligibility criteria must be stored with the source documentation at the study site.

Deviation from any entry criterion excludes a patient from enrollment into the study.

Commercially Confidential Information

Part B

In Part B, the study population will be comprised of male and female patients with knee OA (K&L 2-3). A total of approximately 75 patients will be enrolled in the study and randomized. At least 69 patients are expected to complete the study (10% drop out rate). Additional patients may be enrolled if the dropout rate will exceed 10%. The investigator must ensure that all patients included in the study meet the eligibility criteria. No additional criteria should be applied by the investigator, in order that the study population will be representative of all eligible patients. Patient selection is to be established by checking through all eligibility criteria at screening and before dosing. A relevant record (e.g. checklist) of the eligibility criteria must be stored with the source documentation at the study site.

In total, 135 patients are expected to be randomized into the study.

Deviation from any entry criterion excludes a patient from enrollment into the study.

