6.2.2 Part B

Subjects will be assigned to one of the following three treatment arms in a ratio of "1:1:1" Study treatments are defined as:

•	A: single i.a. injection of 20 mg LNA043,	Commercially Confidential Information
•	B: single i.a. injection of 40 mg LNA043,	Commercially Confidential Information
•	C: single i.a. injection of placebo	Commercially Confidential Information

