1.4.2 Part B

Approximately 75 patients will be enrolled in Part B and randomized. This is a non- confirmatory, randomized, placebo-controlled, patient and investigator blinded study in patients with Kellgren & Lawrence (K&L) with grade 2 or 3 with osteoarthritis (OA). At least 69 patients are expected to complete the study (10% drop out rate). Additional patients may be enrolled if the dropout rate will exceed 10%. Participants will be treated at four treatment visits.

Patients will be assigned to one of the following “three (3)” treatment arms in a ratio of “1:1:1, A:B:C”.

Study treatments are defined as:

A: single i.a. injection of 20 mg (4mL) LNA043, every 4 weeks	CCI
B: single i.a. injection of 40 mg (4mL) LNA043, every 4 weeks	CCI
C: single i.a. injection of placebo (4mL) every 4 weeks	CCI

Commercially Confidential Information

Commercially Confidential Information

2 First interpretable results (FIR)

Commercially Confidential Information

3 Interim analyses

Commercially Confidential Information

4 Statistical methods: Analysis sets

For subjects for which the actual treatment received does not match the randomized treatment the treatment actually received will be used for the analysis.

The safety analysis set will include all subjects that received any study drug.

The PK analysis set will include all subjects with at least one available valid (i.e. not flagged for exclusion) PK concentration measurement, who received any study drug and experienced no protocol deviations with relevant impact on PK data.

The pharmacodynamic (PD) analysis set will include all subjects with available PD data and no protocol deviations with relevant impact on PD data.

The analysis sets and protocol deviation codes are related as follows:

Table 4-1: Protocol deviation codes and analysis sets for Part A and Part B

Category Deviation code	Text description of deviation	Data exclusion
Subjects are excluded from PK analysis in case of these PDs:		
INCL01	Deviation from inclusion criterion 1	Yes
TRT01	Study treatment deviation, i.e. subject did not receive any study treatment or did not complete the full treatment (Part A) Major study treatment deviation i.e. subject did not receive the same dose throughout the study (Part B)	Yes
Subjects are excluded from PD analysis in case of these PDs:		
INCL01	Deviation from inclusion criterion 1	Yes

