5.1 Descriptive analyses

Due to a limited PK sampling, only summary statistics of measured PK concentrations will be reported, and no further PK parameters will be determined for this study.

LNA043 and ANGPTL3 serum and synovial fluid concentration data will be listed by subject, and visit/sampling time point, separately for each study part. Descriptive summary statistics will be provided by treatment, study part and visit/sampling time point, including

Commercially Confidential Information

Summary statistics will include mean (arithmetic and geometric), Standard Deviation (SD), CV (arithmetic and geometric), median, minimum and maximum.

The PK analysis will be done separately for part A and part B.

6 Statistical methods for Pharmacodynamic (PD) parameters

All subjects within the PD analysis set will be included in the efficacy PD data analysis, unless otherwise stated. For MRI related assessments, all subjects within the PD analysis set and subjects who completed Week 28 and/or Week 52, for Part B will be included.

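### Do Part B's approximately 75 randomised, at least 69 completers and 10% drop-out contradict each other in a way that matters?

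*Protocol*

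**What the plan says.** Protocol Section 4 (Population), Part B, states: "A total of approximately 75 patients will be enrolled in the study and randomized". It continues: "At least 69 patients are expected to complete the study (10% drop out rate". The same paragraph allows for topping up: "Additional patients may be enrolled if the dropout rate will exceed 10" per cent. SAP Section 1.4.2 repeats the completer figure, the drop-out rate and the top-up rule, and opens with: "Approximately 75 patients will be enrolled in Part B and randomized".

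For Part A, protocol Section 4 plans about 60 patients and says: "At least 48 patients are expected to complete the study (20% drop out rate". For both parts together it says: "In total, 135 patients are expected to be randomized into the study".

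Allocation in Part B is 1:1:1 over three arms (protocol Section 6.2.2). The Part B sample size calculation (protocol Section 11.9.2) is redacted, so the visible text does not show how 69 was obtained or whether it is the number on which power was based.

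**The concern.** The three Part B figures look like one calculation, but they do not satisfy it. At 10% drop-out, 75 patients yield fewer than 69 completers; to keep 69 of 75, drop-out must be 8%. Part A shows that the same paragraph can get this right, and there the completer figure and the 20% trigger for extra enrolment coincide. In Part B they do not: seven drop-outs leave 68 completers, one short of 69, at a rate that has not passed 10%.

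If 69 were a number that the analysis needed, the plan could fall short of it without its own safeguard applying, and a reader could not tell whether 69 or 10% is the planning figure. The mismatch also appears in both documents, so neither corrects the other.

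**Working it through.** **Inputs.** Part B: N of about 75, completers of at least 69, drop-out d = 10%, three equal arms (protocol Sections 4 and 6.2.2; SAP Section 1.4.2). Part A: N of about 60, completers of at least 48, d = 20% (protocol Section 4).

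**1. Can 69 be reproduced?** Completers = N x (1 - d).

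- Part A: 60 x 0.80 = 48. Exact.
- Part B, whole sample: 75 x 0.90 = 67.5, which is 1.5 below 69.
- Part B, by arm: 75/3 = 25; 25 x 0.90 = 22.5, rounded up to 23; 23 x 3 = 69. Exact.

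The per-arm route reaches the stated number, but it is an inference, since the calculation is redacted.

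**2. What would make the three figures agree?**

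- Keep 75 and 69: d = 1 - 69/75 = 8.0%, or 6 drop-outs.
- Keep 69 and 10%: 69/0.90 = 76.7, so 77 randomised (78 for equal arms of 26).
- Keep 75 and 10%: 67 or 68 completers.

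The discrepancy is therefore about two patients, whichever figure is moved.

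**3. Effect of reading 75 as approximate.**

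| Randomised | Completers at 10% drop-out | Drop-out that leaves 69 |
|---|---|---|
| 75 | 67.5 | 8.0% |
| 76 | 68.4 | 9.2% |
| 77 | 69.3 | 10.4% |

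One or two patients more than 75 close the gap.

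**4. The top-up trigger, with exactly 75 randomised.**

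| Drop-outs | Rate | Completers | Above 10%? |
|---|---|---|---|
| 6 | 8.0% | 69 | No |
| 7 | 9.3% | 68 | No |
| 8 | 10.7% | 67 | Yes |

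Only one outcome falls between the two figures. If drop-out is binomial at 10% (an assumption), exactly 7 drop-outs has probability 0.154, and 6 or fewer has probability 0.367. Part A's chance of at least 48 completers, binomial at 20%, is 0.576.

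**5. Does the completer number enter the analysis?** Study completion is tied to the Week 52 visit (protocol Section 7.1). For the Part B MRI endpoints, SAP Section 6 takes in the PD analysis set and "subjects who completed Week 28 and/or Week 52, for Part B will be included". A patient who leaves after the Week 28 scan is not a completer but still contributes data.

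**6. Effect on power.** No Part B power statement is visible. Suppose that 23 per arm had been powered at 80% or 90% with a two-sample t-test at one-sided alpha 0.05. At 22.5 per arm, power would be 79.2% or 89.4%, a loss of 0.8 or 0.6 percentage points.

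**The case for a change.** The strongest case for a change is that the division is not in dispute: for 75 patients, 69 completers and 10% drop-out cannot all hold, in either document. The word approximately excuses this only in part. Part A also uses it, yet its figures agree exactly, and protocol Section 4 and SAP Section 1.4 give the total of 135 (60 + 75) without that qualifier, although the protocol synopsis includes it. Per-arm rounding would explain where 69 came from without making it consistent, because 23 of 25 is still 8% drop-out, and rounding an expected count up sits badly with a figure introduced as a lower bound. At the planned rate, Part B would reach 69 completers with probability of only about 37%. A one-line correction would cost nothing.

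What stands is that 69 is a little optimistic and that its rounding is not stated. What does not stand is the step from there to a flaw in the plan. The sentence describes an expectation; nothing visible obliges the sponsor to obtain 69 completers. Extra enrolment is permitted above 10%, not required, so the 68-completer outcome leaves no duty unmet. The 37% mostly reflects the expectation being set 1.5 patients high: the chance of 68 or more is 0.367 + 0.154 = 0.521, close to Part A's 0.576.

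Nor is a correction quite free. Changing the expected number to 67 would imply 10.7% drop-out, itself above the trigger. Lowering 69 at all without sight of the redacted calculation could cut a number chosen for power.

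**Conclusion.** The observation is arithmetically correct but clerical, and the plan needs no change. The gap is 1.5 completers, or 2 percentage points of drop-out, on a sample size given as approximate. It is what rounding up in each of three arms would produce. Under the power assumption above, it is worth less than one percentage point.

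The completer count does not define the analysed population, the top-up is discretionary, and the study is non-confirmatory. No analysis, decision rule or conclusion in the visible text depends on whether 67, 68 or 69 patients complete.

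This rests on two things that cannot be confirmed: the per-arm origin of 69, and the absence of a requirement for 69 completers in the redacted Section 11.9.2. If the documents are reopened for another reason, the wording could be tidied after checking it against that section.

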4.1 Inclusion criteria

Patients eligible for inclusion in this study must fulfill all of the following criteria:

- 1. Written informed consent must be obtained before any study-related assessment is performed.
- 2. Able to communicate well with the investigator, to understand and comply with the requirements of the study.
- 3. **Part A:** Patient is ≥ 18 and ≤ 55 years old at time of screening.
 - **Part B:** Patient is ≥ 18 and ≤ 75 years old at time of screening.
- 4. **Part A:** Patient has a body mass index (BMI) \leq 30 kg/m² at screening. For patients with a BMI \geq 30 but \leq 33 kg/m², eligibility has to be confirmed by consultation with the sponsor.
 - **Part B:** Patient has a body mass index (BMI) \leq 35 kg/m² at screening.
- 5. **Part A ONLY:** Patient has a symptomatic, single, partial thickness articular cartilage defect of one knee, grade II or IIIA according to the ICRS classification, localized to either the femoral condyles/femoral trochlea or to the patella, based on MRI or arthroscopy performed within 9 months before screening visit and confirmed by screening 3T MRI.
- 6. **Part A ONLY:** Patient has an onset of pain and impairment of function between two (2) months and two (2) years before screening.
- 7. Commercially Confidential Information
- 8. **Part B ONLY:** Diagnosis of femorotibial OA in the target knee by standard American College of Rheumatology (ACR) criteria at study start (clinical AND radiographic criteria)
- 9. **Part B ONLY:** Patient has a K&L grade 2 or 3 OA of the knee as detailed below according to Schiphof et al (2008)) with JSW 2.00-4.00 mm CCI
- 10. **Part B ONLY:** Patient must have symptomatic disease predominantly in one (the index) knee, with minimal or no symptoms in the contralateral knee. Symptomatic disease is defined as having pain in the knee more than 50% of the days during the last 3 months from screening, according to PI's evaluation.

4.2 Exclusion criteria

Patients fulfilling any of the following criteria are not eligible for inclusion in this study:

- 1. Use of other investigational drugs within 5 half-lives of enrollment, or until the expected pharmacodynamic effect has returned to baseline, whichever is longer.
- 2. History of hypersensitivity to any of the study treatments or excipients or to drugs of similar chemical classes.
- 3. History or current diagnosis of ECG abnormalities indicating significant risk of safety for patients participating in the study such as:
 - Concomitant clinically significant cardiac arrhythmias, e.g. sustained ventricular tachycardia, and clinically significant second or third degree AV block without a pacemaker
 - Personal history or family history of long QT syndrome or Torsades de Pointes
- 4. History of immunodeficiency diseases, including a positive HIV (ELISA and Western blot) test result.
- 5. Chronic infection with Hepatitis B (HBV) or Hepatitis C (HCV). A positive HBV surface antigen (HBsAg) test, or if standard local practice, a positive HBV core antigen test, excludes a patient. Patients with a positive HCV antibody test should have HCV RNA levels measured. Patients with positive (detectable) HCV RNA should be excluded.
- 6. History of malignancy of any organ system (other than localized basal or squamous cell carcinoma of the skin or *in-situ* cervical cancer), treated or untreated, within the past 5 years, regardless of whether there is evidence of local recurrence or metastases.
- 7. Pregnant or nursing (lactating) women.
- 8. Women of child-bearing potential, defined as all women physiologically capable of becoming pregnant, unless they are using highly effective methods of contraception during dosing and for 15 days after stopping of investigational drug. Highly effective contraception methods include:
 - Total abstinence from heterosexual intercourse (when this is in line with the preferred and usual lifestyle of the patient). Periodic abstinence (e.g. calendar, ovulation, symptothermal, post-ovulation methods) and withdrawal are not acceptable methods of contraception.
 - Female sterilization (have had surgical bilateral oophorectomy with or without hysterectomy), total hysterectomy or tubal ligation at least six weeks before taking investigational drug. In case of oophorectomy alone, only when the reproductive status of the woman has been confirmed by follow up hormone level assessment.
 - Male sterilization (at least 6 months prior to screening). For female patients on the study the vasectomized male partner should be the sole partner for that patient.
 - Use of oral, injected or implanted hormonal methods of contraception or placement of an intrauterine device (IUD) or intrauterine system (IUS) or other forms of hormonal contraception that have comparable efficacy (failure rate <1%), for example hormone vaginal ring or transdermal hormone contraception

Novartis

In case of use of oral contraception, women should be stable on the same pill for a minimum of 3 months before taking investigational drug.

Women are considered post-menopausal and not of child bearing potential if they have had 12 months of natural (spontaneous) amenorrhea with an appropriate clinical profile (e.g. age appropriate, history of vasomotor symptoms) or have had surgical bilateral oophorectomy (with or without hysterectomy), total hysterectomy or tubal ligation at least six weeks ago. In the case of oophorectomy alone, only when the reproductive status of the woman has been confirmed by follow up hormone level assessment is she considered not of child bearing potential.

9. Part A: Regular smokers (> 5 cigarettes or equivalent use of tobacco products per day in the previous 3 months). Urine cotinine levels will be measured during screening for all patients. Regular smokers will be defined as any patient who reports tobacco use of > 5 cigarettes or equivalent/day and/or who has a urine cotinine \geq 500 ng/mL.

Part B: Regular smokers (> 10 cigarettes or equivalent use of tobacco products per day in the previous 3 months).

10. **Part A:** Use of prohibited medications:

Commercially Confidential Information

Part B: Use of prohibited medications:

- 11. Patient has a known autoimmune disease susceptible to immunosuppressive treatment, inflammatory arthropathy (including but not limited to rheumatoid arthritis, psoriatic arthritis, ankylosing spondylitis, CPPD, gout), active acute or chronic infection of the joint, Lyme disease involving the knee, systemic cartilage disorder, or a known systemic connective tissue disease.
- 12. Patient unable to undergo MRI or presents absolute contraindications to MRI (e.g., metallic implants, metallic foreign bodies, pacemaker, defibrillator).
- 13. Commercially Confidential Information
- 14. Part A ONLY: Patient has radiologically apparent degenerative joint disease in the target knee as determined by Kellgren and Lawrence grade ≥2 based on X-ray evaluation performed within 9 months from screening.
- 15. Patient has had surgical treatment of the target knee using mosaicplasty, microfracture, meniscectomy >50% (Note: prior diagnostic arthroscopy with debridement and lavage, <50% meniscectomy, lateral release, patellar realignment, medial patellofemoral ligament reconstruction are acceptable if performed at least 2 months prior to screening; anterior cruciate ligament reconstruction is acceptable if performed 12 months prior to screening, or less if restoration of joint function is evident, and agreed by the sponsor).

- 16. Patient has an unstable target knee joint (including but not limited to posttraumatic or congenital laxity) or insufficiently reconstructed ligaments based on medical history and physical examination by the investigator.
- 17. **Part A ONLY:** Patient has patellofemoral dysplasia Dejour Grade B-D based on X-ray or MRI evaluation.
- 18. Part A: Patient has malalignment (valgus- or varus-deformity) in the target knee $\geq 5^{\circ}$ based on X-ray evaluation. In suspected cases, the mechanical axis must be established radiographically through complete leg imaging during standing and in PA projection.
 - **Part B:** Patient has malalignment (valgus- or varus-deformity) in the target knee > 7.5° based on X-ray evaluation. In suspected cases, the mechanical axis must be established radiographically through complete leg imaging during standing and in PA projection.
- 19. Vulnerable subjects, e.g. subjects kept in detention, soldiers, employees of the sponsor or a clinical research organization, involved in this study
- 20. History of drug abuse or unhealthy alcohol use within the 12 months prior to dosing, or evidence of such abuse as indicated by the laboratory assays conducted during screening. Unhealthy alcohol use is defined as a history of, or current alcohol misuse/abuse, defined as five or more drinks on the same occasion on each of 5 or more days in the past 30 days.
- 21. **Part B (ONLY):** Patients with Nephrotic syndrome and/or significant proteinuria ($\geq 3+$ on dipstick or protein-creatinine ratio ≥ 1 g/g Cr) at screening
- 22. **Part B (ONLY):** History of coagulopathy or medical condition requiring anticoagulation which would preclude knee injection (antiplatelet or anticoagulant treatment [for patients using warfarin, INR to be <3 prior to injection], is allowed).
- 23. Part B (ONLY): Clinical signs of inflammation (i.e., redness) in the target knee.
- 24. Part B (ONLY): History of knee replacement (unilateral or total) in either knee.
- 25. **Part B (ONLY):** Presence of severe hip OA conditioning lower limb function according to PI's evaluation.

No additional exclusions may be applied by the investigator, in order to ensure that the study population will be representative of all eligible patients.

5 Restrictions for Study Subjects

During recruitment, screening/informed consent review, the subjects must be informed and reminded of the restrictions outlined in this section.

5.1 Contraception requirements

Women of child bearing potential must be informed that taking the study treatment may involve unknown risks to the fetus if a pregnancy was to occur during the study, and agree that in order to participate in the study they must adhere to the contraception requirement during dosing and for 15 days after stopping of investigational drug.

If there is any question that the subject will not reliably comply, the subject should not be entered or continue in the study. Male subjects should be informed that if a female partner becomes pregnant while he is enrolled in the study, contact with the female partner will be attempted to request her consent to collect pregnancy outcome information. Please refer to exclusion criteria (Section 4.2) for details of contraception requirements for the study.

5.2 Prohibited treatment

Use of the treatments displayed in the table below is NOT allowed in the reported timeframe. If required outside of the definitions of Rescue medication (see Section 6.10), subject has to be discontinued from study drug, but will continue the study until V399.

Table 5-1 Prohibited treatment Part A

Medication	Prohibited period	Action to be taken
Local i.a. treatment into the knee, including but not restricted to viscosupplementation and corticosteroids (impact on tissue repair/confounding of efficacy)	CCI	discontinue study treatment
Corticosteroid use by any route except topical (impact on tissue repair)	CCI	discontinue study treatment
Nonsteroidal anti-inflammatory drugs (NSAIDs), including aspirin (greater than 100 mg/day) by any route except topical (impact on cartilage tissue repair). See Section 6.10 (Rescue medication) for exceptions	CCI	Must be recorded on the Concomitant medications/ Significant non-drug therapies section of the CRF.
Paracetamol greater than 3000 mg per day (confounding of liver function) See Section 6.10 (Rescue medication) for exceptions	CCI	Must be recorded on the Concomitant medications/ Significant non-drug therapies section of the CRF.
Oral glucosamine, chondroitin sulfate, or any nutraceutical with potential activity on cartilage repair (confounding of efficacy)	CCI	Must be recorded on the Concomitant medications/ Significant non-drug therapies section of the CRF.
Paracetamol and/or NSAIDs are not allowed during seven days before visit 201, 202, 299 and V399 CCI	CCI	PRO to be performed ≥ 7 days post last paracetamol/ NSAID intake, but ≤2 weeks after planned visit date.

Prohibited treatment Part B Table 5-2

Medication	Prohibited period	Action to be taken
Local i.a. treatment into the knee, including but not restricted to viscosupplementation and corticosteroids (impact on tissue repair/confounding of efficacy)	CCI	discontinue study treatment
Long-term treatment (>14 days) with oral corticosteroids >5 mg/day.	CCI	Must be recorded on the Concomitant medications/ Significant non-drug therapies section of the CRF.
Paracetamol greater than 3000 mg per day (confounding of liver function) See Section 6.10 (Rescue medication) for exceptions	CCI	Must be recorded on the Concomitant medications/ Significant non-drug therapies section of the CRF.
Oral glucosamine, chondroitin sulfate, or any nutraceutical with potential activity on cartilage repair (confounding of efficacy)	CCI	Must be recorded on the Concomitant medications/ Significant non-drug therapies section of the CRF.

Note: The use of oral corticosteroids (≤5 mg/day oral prednisone or equivalent) for an indication other than OA pain will be allowed during the trial. In addition, short-term use of any tapering course of oral corticosteroids for \leq 14 days will be allowed. Topical corticosteroids are allowed.

